8.2.3. Symptom Outcome

The percentage of subjects with complete resolution of symptoms at the Follow-up (FU) visit will be analyzed by Candida Species of the baseline yeast and overall, using the same inferential analysis employing the same methods as for the primary analysis as noted in Section 8.1.1. The subjects with missing Follow-Up data for the symptom outcome will be imputed as symptom persistence using the NRI method described in Section 4.4.

Symptom outcomes will be assessed at the FU Visit according to the following definitions:

- Symptom Resolution: All symptoms are absent (score = 0) without need for further antifungal treatment or topical vaginal drug therapy for the treatment of vulvovaginal irritation/pruritus prior to or at FU visit;
- Symptom Persistence: No response to therapy or incomplete resolution of symptoms or use of additional vulvovaginal or systemic antifungal therapy or topical vaginal drug

therapy for the treatment of vulvovaginal irritation/pruritus prior to or at FU visit. For the subject who early terminated before the FU visit and received additional vulvovaginal or systemic antifungal therapy or topical vaginal drug therapy for the treatment of vulvovaginal irritation/pruritus prior to or at the early termination visit, the subject is considered a symptom persistence.

In addition, a sensitivity analysis will be conducted based on the mITT set where the subjects with the imputed symptom outcome using the NRI method at the FU visit will be removed from the analysis.

8.2.4. Clinical Improvement

The percentage of subjects with clinical improvement (partial or complete resolution of signs and symptoms with total composite score no greater than 1 without need for further antifungal treatment and topical vaginal drug therapy for the treatment of vulvovaginal irritation/pruritus prior to or at TOC visit) at the TOC visit will be analyzed using the same inferential analysis employing the same methods as for the primary analysis as noted in Section 8.1.1. For the subject who early terminated before the TOC visit and received additional vulvovaginal or systemic antifungal therapy or topical vaginal drug therapy for the treatment of vulvovaginal irritation/pruritus prior to or at the early termination visit, the subject is considered no clinical improvement. The subjects with missing TOC visit data for clinical improvement outcome will be imputed as no clinical improvement using the NRI method described in Section 4.4. The composite score will be calculated as the rules described in Section 8.1.

In addition, a sensitivity analysis will be conducted based on the mITT set where the subjects with the imputed clinical improvement outcome using the NRI method at the TOC visit will be removed from the analysis.

8.2.5. Composite Score of the Vulvovaginal Signs and Symptoms

The following secondary efficacy endpoints will be analyzed using an analysis of covariance (ANCOVA) model having treatment group, site and diabetes mellitus diagnosis (Yes or No) as classification variables, and the baseline value as the continuous covariate.

- The change in signs and symptoms score from Baseline to TOC visit;
- The change in signs and symptoms score from Baseline to FU visit.

For each treatment and treatment comparison versus placebo, the least squares mean, associate standard error (SE), 95% confidence interval and corresponding p-value will be presented.

A descriptive summary will be presented for the followings based on the mITT and PP sets:

- The change in total sign score from baseline to TOC and FU visits;
- The change in total symptom score from baseline to TOC and FU visits;
- The change in signs and symptoms score from TOC to FU visit.

A listing will be provided to present the signs and symptoms score and mycological outcome for all subjects in the ITT set. Assessments that are not done will be presented in the data listing with a missing value.

9. Safety Analysis

Safety analyses will be performed on all subjects in the safety set. Analyses will be based on adverse events, vital signs, clinical laboratory assessments, and physical examination findings. Safety analyses in general will be descriptive and will be presented in tabular format with the appropriate summary statistics by treatment group.

Individual subject listings will be provided to support the tables.

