At Day 10, the TOC visit, the 600-mg dose showed clinical and mycological response rates in-line with the reference fluconazole arm. Specifically, the clinical cure was reported in 14 of 27 of patients (52%) in the 600-mg dose and in 14 of 24 of patients (58%) in the fluconazole arm. The percentage of patients showing 0 or 1 signs and symptoms score was also comparable, with 70% and 71% of patients reporting this improvement in the ibrexafungerp (SCY-078) 600-mg dose and fluconazole arms, respectively. The mycological eradication at this timepoint was 63% for both groups.

At Day 25, the follow-up (FU) visit, the ibrexafungerp (SCY-078) 600-mg dose showed a trend towards improved clinical and mycological outcomes when compared to the fluconazole arm. If patients had persistence or recurrence of signs and symptoms of VVC, rescue antifungal medication could be prescribed. Seven (7) patients treated with fluconazole received rescue antifungal medication, whereas one patient treated with ibrexafungerp (SCY-078) 600 mg received rescue antifungal medication. The rate of patients with zero signs and symptoms at the FU visit was 70% for the ibrexafungerp (SCY-078) 600-mg dose versus 50% for the fluconazole arm. A similar difference was observed with the "0 or 1 signs and symptoms score" analysis, with 82% of patients achieving this improvement with the ibrexafungerp (SCY-078) 600-mg dose versus 58% with fluconazole. The mycological eradication at this timepoint was also numerically higher in the 600-mg dose (48%) when compared to the fluconazole arm (38%).

Oral ibrexafungerp (SCY-078) 600-mg dose was generally well tolerated, with self-limiting (generally one-day duration), mild to moderate gastrointestinal adverse events (AEs) being the most commonly reported. Nausea was reported in three patients (10%) in the ibrexafungerp (SCY-078) 600-mg dose arm compared to two patients (6%) in the FLU arm. Diarrhea and loose stool was reported in five patients (17%) in the ibrexafungerp (SCY-078) 600-mg dose arm compared to one patient in the FLU arm (3%). Abdominal pain was reported in one patient (3%) in the ibrexafungerp (SCY-078) 600-mg dose arm compared to 5 patients (16%) in the FLU arm. No vomiting, severe AEs or discontinuations due to AEs were reported in the ibrexafungerp (SCY-078) 600-mg dose arm.

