Unless otherwise specified, baseline will be defined as the last non-missing assessment prior to or on the date (and time if appropriate) of the first dose of study drug. Change from baseline is defined as: post-baseline value – baseline value.

The study day will be calculated as follows:

If the assessment date occurs on or after the date of the first dose of study drug:

$$\text{Study day} = \text{assessment date} - \text{first dose date} + 1.$$

If the date of interest occurs before the date of the first dose of study drug:

$$\text{Study day} = \text{assessment date} - \text{first dose date}$$

There is no study day 0.

All analyses will be conducted using SAS Version 9.3 or higher. All statistical tests will be two-sided and interpreted at a 5% significance level.

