4.1. Sample Size

The primary endpoint of the study is the percentage of subjects achieving a clinical cure at the TOC visit. Assuming clinical cure rates of 50% and 30% for ibrexafungerp and placebo administered in a 2:1 ratio, respectively, approximately 282 subjects will provide 90% power to detect a difference between ibrexafungerp and placebo based on a Pearson’s Chi-squared test with a Type 1 error rate of 5%. Because it is expected that approximately 20% of subjects may not have a mycological culture-confirmed infection at Baseline and approximately 10% may withdraw early

from the study, an additional 84 subjects are added for a total of 366 subjects (244 subjects randomized to ibrexafungerp and 122 subjects, to placebo).

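### The change-score ANCOVA pools one residual variance under 2:1 allocation, so its confidence interval may be somewhat too narrow if ibrexafungerp scores are the less variable

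*SAP*

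**What the plan says.** SAP 8.2.5 analyses the change in composite score from baseline to test of cure (TOC) and to follow-up (FU) with "an analysis of covariance (ANCOVA) model having treatment group, site and diabetes mellitus diagnosis (Yes or No) as classification variables". A woman's score at baseline also enters the model, as a continuous term. For each arm and for the comparison with placebo, "the least squares mean, associate standard error (SE), 95% confidence interval and corresponding p-value will be presented". SAP section 4 adds: "All statistical tests will be two-sided and interpreted at a 5% significance level".

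No variance structure, robust standard error or sensitivity analysis is named for this endpoint. Protocol 18.6.2 had a two-way ANOVA, which also pools the variance. SAP section 11 explains the move to ANCOVA and leaves room for further variables at blinded review, but says nothing about variance.

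The facts that bear on spread are these:

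- The score runs from 0 to 18 (SAP 8.1).
- The sample size in SAP 4.1 is set "Assuming clinical cure rates of 50% and 30% for ibrexafungerp and placebo administered in a 2:1 ratio, respectively", with "244 subjects randomized to ibrexafungerp and 122 subjects, to placebo".
- In Phase 2b (Protocol 7.1) this dose gave clinical cure in 14 of 27 women. For a score of 0 or 1 the text reports the ibrexafungerp and fluconazole arms together, "with 70% and 71% of patients reporting this improvement".
- At FU, a symptom-free woman whose signs were not rated scores 0 by rule (SAP 8.1).

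**The concern.** A score that cannot fall below 0 tends to bunch at 0 in the arm that does better. Here that arm is also twice the size of the other. The pooled variance is then weighted towards the larger arm, while the true variance of the difference is driven mainly by the smaller one. If the larger arm is the less variable, the reported standard error is too small and the nominal 95% interval covers the true difference less than 95% of the time.

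What is at stake is the stated precision of a secondary efficacy estimate when the drug works, which is when the interval will be quoted. The standard errors of the two arm means are affected as well.

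**Working it through.** **1. The plan's own figure.** The documents give no SD, power or precision for the change score, so the only figure to reproduce is the primary sample size: "approximately 282 subjects will provide 90% power to detect a difference between ibrexafungerp and placebo". With p̄ = (2×0.5 + 0.3)/3 = 0.433, the placebo number is [1.96·√(p̄(1−p̄)×1.5) + 1.2816·√(0.5×0.5/2 + 0.3×0.7)]² / 0.2² = 93.2. This rounds up to 94, so the total is 94 + 188 = 282, as stated (power 90.2%).

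**2. Pooled against true standard error.** Let s₁, n₁ refer to ibrexafungerp and s₂, n₂ to placebo.

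- Pooled SE² = [(n₁−1)s₁² + (n₂−1)s₂²]/(n₁+n₂−2) × (1/n₁ + 1/n₂)
- True SE² = s₁²/n₁ + s₂²/n₂

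With n₁ = 2n₂ the pooled form is close to s₁²/n₂ + s₂²/n₁, so the weights are swapped. With 1:1 allocation the two forms agree. Coverage is 2Φ(1.96 × pooled SE/true SE) − 1. At 188:94:

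| SD ratio, drug/placebo | Pooled/true SE | Coverage |
|---|---|---|
| 1.0 | 1.000 | 95.0% |
| 0.9 | 0.965 | 94.2% |
| 0.8 | 0.929 | 93.1% |
| 0.7 | 0.891 | 91.9% |
| 0.6 | 0.853 | 90.6% |

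At ratios 0.8 and 0.6, splits of 195:98, 176:88 and 244:122 give the same coverage to within 0.1 point. For the arm means at ratio 0.7, ignoring covariates, the pooled SD is √((187×0.49 + 93)/280) = 0.812 of the placebo SD. The placebo SE is then about 19% too small and the ibrexafungerp SE about 16% too large (0.812/0.7 = 1.16).

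**3. What SD ratio is plausible at TOC?** Take cure as score 0. Let π be the share at zero, and let non-zero scores have mean m and coefficient of variation c. The variance is m²(1−π)(π + c²). With π = 0.5 and 0.3, and the drug's non-zero mean k times the placebo's, the SD ratio is k·√[0.5(0.5 + c²) / (0.7(0.3 + c²))]. Neither c nor k is in the documents. Each cell gives the SD ratio, then coverage:

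| k | c = 0.2 | c = 0.447 | c = 1.0 |
|---|---|---|---|
| 1.0 (only the zeros differ) | 1.065, 95.5% | 1.000, 95.0% | 0.908, 94.2% |
| 0.9 | 0.959, 94.7% | 0.900, 94.2% | 0.817, 93.3% |
| 0.8 | 0.852, 93.7% | 0.800, 93.1% | 0.726, 92.3% |
| 0.7 | 0.746, 92.5% | 0.700, 91.9% | 0.635, 91.1% |

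At k = 1 the ratio crosses 1 where 0.25 + 0.5c² = 0.21 + 0.7c², that is, at c = √0.2 = 0.447. Below that, the pooled interval is slightly too wide.

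Phase 2b gives a hint about c. About 19 of 27 women (70%) scored 0 or 1 and 14 were cured, so about 5 of the 13 not cured scored 1 and 8 scored 2 or more. If all eight scored 3, c = 0.44; if all scored 4, c = 0.51; any spread raises it. That points to a ratio a little below 1.

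**4. Simulation of the SAP model.** This used 4,000 trials per scenario, 282 women, 27 sites, and diabetes and baseline in the model. The assumed baseline was mean 10.4, SD 3.2, with 9% diabetic.

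- Cure 50% against 30%, non-cured women alike: SD ratio 0.97, coverage 95.1%. With tightly clustered non-cured scores: ratio 1.03, coverage 95.6%.
- Cure 50 to 52% against 30%, drug also lowering non-cured scores (65 to 75% of the drug arm at 0 or 1): ratio 0.58 to 0.77, coverage 91.2 to 92.7%. HC2 robust standard errors gave 94.1 to 95.0%.
- No treatment effect: coverage 95.0%.

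A second simulation (2,500 trials per scenario, 195:98, 30 unequal sites) gave 91.4 to 95.0% with the pooled variance and 94.1 to 95.2% with arm-specific variances. Rejection under no effect was 0.049 and 0.051 respectively.

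**The case against.** The strongest objection is that the premise is assumed. No SD appears for either arm, and the only placebo figure is the 30% cure assumption. The Phase 2b comparison was with fluconazole, so it says nothing about placebo spread. On the documented inputs alone the effect almost vanishes. A reader might infer that a higher share at the floor is enough to make the interval materially too narrow. It is not: with only the zeros differing, coverage is 94.2 to 95.5%. The figures near 91 to 92% need the further assumption that the drug also lowers scores in women not cured. That is plausible, but no document gives a number for it.

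A reader might also carry these figures over to FU, where the zero-by-rule scoring adds mass at the floor. The documents do not support that. Under Protocol 11.4 a woman rescued before or at TOC has no further visit, and SAP 4.4 covers only categorical endpoints, so no imputation is stated for the change score. If early failures fall more often on placebo, their absence could shrink the placebo spread. Neither simulation modelled this.

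Finally, clinical cure, clinical improvement (score 0 or 1) and symptom resolution at FU are analysed as binary outcomes by CMH and need no common residual variance. Ordinary ANCOVA on a bounded score is also conventional.

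All of this stands as a limit on size and priority. It does not touch the algebra: under 2:1 allocation the pooled standard error is wrong whenever the variances differ, and nothing else in the plan corrects it.

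**Conclusion.** The point holds as a minor one. The interval for the difference in change score may be somewhat too narrow if the ibrexafungerp arm has the smaller residual variance. At TOC, coverage is about 94 to 95.5% if only the share at zero differs, and about 91 to 94.7% if the drug also lowers non-cured scores by 10 to 30%. Both ranges assume a non-cured coefficient of variation of 0.2 to 1.0, and that raw SD ratios stand in for residual ones. FU is left unquantified.

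Two stronger readings fail. The type I error is not inflated when the drug does nothing, because the arms then share one distribution. The primary CMH analysis of clinical cure is untouched.

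**What to change.** In SAP 8.2.5 keep treatment, site, diabetes and baseline, but estimate a separate residual variance per arm: PROC MIXED with REPEATED / GROUP=treatment and Satterthwaite or Kenward-Roger degrees of freedom. Take the SE, 95% interval and p-value at TOC and FU from that model. HC3 standard errors on the existing model are an acceptable alternative. Make the choice before unblinding, since choosing after seeing the arm SDs would be post hoc.

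The cost is one sentence and one SAS option. When the variances differ, the interval widens by about 1 to 13% in the simulations; the extreme cell of the table in step 3 implies about 15% (1/0.867). Power fell only from 82% to 81% in the scenario where it was compared (residual SD 2.3 against 2.5). If the variances turn out equal, almost nothing is lost.

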11.4 Early Termination

With effective oral therapy, immediate relief of all symptoms is not expected and subjects should not expect immediate relief.

If the subject experiences persistence or worsening or recurrence of symptoms that per the investigator's assessment (e.g., symptoms ≥ 3) warrant the use of rescue antifungal therapy, a vaginal examination with investigator's rating of signs should be completed. Additionally, vulvovaginal samples should be obtained for KOH testing and pH measurements by the local laboratory, fungal culture by the central laboratory and investigation of other pathogens such as bacterial vaginosis and *Trichomonas vaginalis* by the local laboratory.

If the KOH test is negative, the investigator should consider other causes for the persistence or worsening of the symptoms as antifungal rescue medication may not be indicated.

If the investigator's rating of the vulvovaginal signs and vaginal sample collection is not possible prior to the initiation of the rescue therapy, it should still be completed as soon as possible after rescue therapy is initiated.

In addition to the vaginal examination, the symptoms that led to the use of rescue antifungal therapy should be documented in the eCRF and the following procedures should also be completed:

- If rescue therapy is administered prior to or at the TOC visit, all TOC visit procedures should be completed and no additional visits will be needed. The subject will be considered as early termination due to lack of efficacy prior to or at TOC.
- If rescue therapy is administered after the TOC visit but prior to or at the FU visit, all FU visit procedures should be completed and no additional visits will be needed. The subject will be considered as early termination due to lack of efficacy after TOC but prior to or at FU.

Oral fluconazole [one 150-mg dose] may be provided to study sites as rescue medication. However, at the investigator's discretion other approved antifungal agent may be administered as rescue medication to a particular patient for whom fluconazole is not considered the optimal option. All rescue antifungal medications should be documented in the eCRF.

Details of study treatment groups and dietary requirements for treatment administration are provided in [Section 12.1](#) and [Section 12.2](#), respectively.

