14.11 Rating of Vulvovaginal Signs by the Investigator Using the VSS Scale

The investigator (or qualified designee) will perform vulvovaginal examinations to rate the subject's signs of infection at the Screening and TOC visits. The vulvovaginal examination will be repeated at the FU visit only if the subject presents symptoms. Otherwise, no additional vulvovaginal examination will be conducted or signs rated. Vulvovaginal examinations may be conducted at unscheduled visits, if needed.

If the subject experiences persistence or worsening or recurrence of symptoms that per the investigator's assessment (e.g. symptoms ≥ 3) warrant the use of rescue antifungal therapy, a

vaginal examination with rating of signs by the investigator should be completed prior to initiation of rescue therapy. If the investigator's rating of the vulvovaginal signs is not possible prior to the initiation of the rescue therapy, it should still be completed as soon as possible after rescue therapy is initiated.

Investigators will assess the signs of infection using the VSS Scale provided in [Section 21.0 \[Appendix B\]](#)), a standardized, predefined scale where each sign of the vagina and/or vulva will be given a numerical rating based on severity, as follows:

- Edema: absent = 0; mild = 1; moderate = 2; severe = 3
- Erythema: absent = 0; mild = 1; moderate = 2; severe = 3
- Excoriation or fissures: absent = 0; mild = 1; moderate = 2; severe = 3

Other findings will be recorded using the most relevant medical term in the abbreviated physical examination page of the eCRF.

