18.6.2 Efficacy Analyses

The efficacy analyses will be conducted using the mITT (primary analysis population), ITT and PP populations to evaluate ibrexafungerp vs. placebo.

The primary endpoint, percentage of subjects with clinical cure at TOC, will be analyzed using a Cochran Mantel Haenszel (CMH) test adjusted for site; the p-value and 95% confidence intervals will be presented. Missing Day 8-Day 14 (TOC) data for the primary endpoint will be imputed as failures in the analysis. A sensitivity analysis will be performed where subjects with missing values will be removed from the analysis. All other data will be analyzed as is with no imputation.

For other continuous efficacy endpoints, a two-way analysis of variance (ANOVA) model will be used including effects for treatment and site; p-values and 95% confidence intervals will be presented. For other categorical endpoints, the CMH test adjusted for site will be performed, and p-values and 95% confidence intervals will be presented.

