4.4. Handing of missing data

For categorical response endpoints including clinical outcome, mycological outcome, symptom outcome, and clinical improvement, subjects will be considered a non-responder for the non-responder imputation (NRI) analysis if they do not meet the clinical response criteria for categorical responses or are missing categorical response data at the specific visit. Randomized subjects without at least 1 post-baseline observation will also be defined as non-responder for the NRI analysis such that subjects who have a missing value at the TOC visit or FU visit will be assigned as treatment failures, i.e., non-responders or positive mycological outcome for the corresponding visit. Randomized subjects without study treatment will be excluded from all analysis.

5. Subject Disposition

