5.1. Disposition

A disposition of subjects includes the number and percentage of subjects for the following categories: subjects in each analysis set (ITT, mITT, PP, SS), subjects who completed TOC visit, subjects who completed the study (without need for antifungal treatment), subjects who completed the study (with need for antifungal treatment at FU visit), subjects who discontinued from the study, and the reasons for study discontinuation will be presented by the ITT and mITT sets. All percentages will be based on the number of subjects in each corresponding set.

The reason for study discontinuation may include any of the following: lack of efficacy and/or use of antifungal therapy prior to TOC; use of antifungal therapy after TOC (but prior to FU visit); adverse event; lack of efficacy after TOC; lost to follow-up; physician decision; pregnancy; study terminated by sponsor; study subject withdrawal by parent or guardian; withdrawal by subject; other; death, and trial screen failure.

Subject disposition data will be presented in a listing.

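### Neither score-change ANCOVA in SAP 8.2.5 has a rescue rule, so women rescued by TOC normally drop out of the Baseline-to-FU comparison, although SAP 8.2.3 counts them as failures (minor; cheap to fix)

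*SAP*

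**What the plan says.** - **Endpoint and model.** SAP 8.2.5 fits an ANCOVA with treatment, site, diabetes and baseline score to the change at TOC and to "The change in signs and symptoms score from Baseline to FU visit". It reports least squares means, a 95% confidence interval and a p-value. It has no rule for rescue or for a missing score.
- **Rescue by TOC.** Protocol 11.4: "all TOC visit procedures should be completed and no additional visits will be needed". The woman is classed as an early termination for lack of efficacy. SAP 5.1 agrees: "The reason for study discontinuation may include any of the following: lack of efficacy and/or use of antifungal therapy prior to TOC".
- **Rescue after TOC.** Protocol 11.4: "all FU visit procedures should be completed and no additional visits will be needed".
- **Timing of the rating.** Protocol 14.11 sets the default: "vaginal examination with rating of signs by the investigator should be completed prior to initiation of rescue therapy". If that is not possible, Protocol 11.4 says of the rating and samples that "it should still be completed as soon as possible after rescue therapy is initiated".
- **Missing data.** SAP 4.4 limits its rule: "For categorical response endpoints including clinical outcome, mycological outcome, symptom outcome, and clinical improvement". Protocol 18.6.2, after the primary endpoint: "All other data will be analyzed as is with no imputation".
- **Zero rule at FU.** SAP 8.1 gives a composite score of zero to a woman with no symptoms and no signs rated at FU.
- **Rescue in the binary endpoints.** SAP 8.1 (clinical cure), 8.2.3 (FU symptoms) and 8.2.4 (clinical improvement) each count antifungal rescue up to and including the visit as failure.
- **Unused method.** The SAP abbreviation list includes mBOCF, modified baseline observation carried forward. No rule in the body of the SAP uses it.

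**The concern.** An ANCOVA needs an observed outcome. A woman with no FU visit and no imputed score contributes nothing to the FU comparison. Whether she is in the analysis depends on whether she failed early enough to be rescued, which is an outcome that the drug is meant to change. The p-value and interval then describe a subset that randomisation no longer balances.

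Women rescued after TOC raise a second problem. They remain in the analysis, and if they were rated after the antifungal took effect, their score reflects the rescue drug. A woman who is symptom-free at FU with no signs rated would enter as a complete response.

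The same opening exists at TOC. A TOC rating made after rescue can enter the Baseline-to-TOC ANCOVA, although SAP 8.1 and 8.2.4 count that woman as a failure.

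At stake is one listed secondary endpoint, and its agreement with the rescue-as-failure approach that the SAP takes for its binary endpoints.

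**Working it through.** **Step 1: the route out of the analysis, and where a late rating can enter.**

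| Woman | Score available | SAP 8.2.5 as written | SAP binary endpoint |
|---|---|---|---|
| Rescued by TOC, at FU | Normally none | Drops out | Persistence (8.2.3) |
| Rescued after TOC, at FU | FU procedures done; rating before or after rescue | Stays in with whichever rating exists | Persistence (8.2.3) |
| Rescued by TOC, at TOC | TOC procedures done; rating before or after rescue | Stays in with whichever rating exists | Failure (8.1, 8.2.4) |

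The SAP does not state the exclusion in words. It follows from the absence of a visit, the absence of imputation and the need for an observed outcome. It holds normally rather than always, because Protocol 11.4 does not forbid a later visit.

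**Step 2: the plan's own figure.** No sample size is stated for the score analysis. The only design figure is 282 evaluable subjects (50% vs 30% cure, 2:1, 90% power, two-sided 5%). The pooled rate is (0.3 + 2 × 0.5)/3 = 0.433. The placebo n is [1.960 × √(1.5 × 0.433 × 0.567) + 1.282 × √(0.21 + 0.25/2)]² / 0.20² = 93.2, so 94. With 188 on drug this gives 282, as stated.

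**Step 3: inputs for an illustration.**
- Cure c = 0.5 on drug and 0.3 on placebo: the planned TOC rates, assumed to hold at FU.
- Drug rescue among non-cures = 1/13 (8%). Protocol 7.1 reports one rescued patient on 600 mg in Phase 2b, with 14 of 27 cured. I assume the denominator is those 27 and that she was one of the 13 non-cures. The text does not say when she was rescued, and there was no placebo arm.
- Placebo rescue among non-cures: 8%, 20% or 30% (assumed).
- Mean change: −9 if cured, −5 if neither cured nor rescued, and s just before rescue (all assumed; no score means are given).

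**Step 4: rescued by TOC and left out.** With rescue share r, let q = (1 − c)r and p = (1 − c)(1 − r).
- Planned mean = (−9c − 5p)/(c + p).
- Rescue-as-failure mean = −9c − 5p + s·q.

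Example with s = −1 and placebo r = 0.20:
- Drug: q = 0.038, p = 0.462. Planned −6.808/0.962 = −7.08; rule −6.85.
- Placebo: q = 0.14, p = 0.56. Planned −5.50/0.86 = −6.40; rule −5.64.
- Drug minus placebo: planned −0.68, rule −1.21, gap 0.52 (from unrounded values).

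| Placebo rescue | Planned difference | Gap, s = 0 | s = −1 | s = −3 | s = −5 |
|---|---|---|---|---|---|
| 8% | −0.81 | 0.07 | 0.05 | 0.02 | −0.01 |
| 20% | −0.68 | 0.62 | 0.52 | 0.32 | 0.12 |
| 30% | −0.56 | 1.10 | 0.93 | 0.58 | 0.24 |

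The table does not set a ceiling: at 50% placebo rescue with s = 0 the gap is 2.1.

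At 8%/20%, the women removed number 188 × 0.5/13 ≈ 7 on drug (4%) and 94 × 0.7 × 0.20 ≈ 13 on placebo (14%).

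**Step 5: rescued after TOC and kept in.** If all are rated before rescue, there is no gap. The worst case scores every such woman zero after rescue (change −9) and gives her the baseline score under the rule (change 0):
- 10% of non-cures in both arms: planned −7.20 + 6.48 = −0.72; rule −6.75 + 5.85 = −0.90; gap 0.18.
- 8%/20%: planned −7.15 + 6.76 = −0.39; rule −6.81 + 5.50 = −1.31; gap 0.91.

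If a pre-rescue rating with change −5 exists instead, the rule gives −7.00 + 6.20 = −0.80 in both settings, and the gaps fall to 0.08 and 0.41.

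**The case against.** The strongest reply is that little depends on this analysis. It is part of the last-listed secondary endpoint, no decision rule rests on it, and the likely bias runs against the sponsor's drug. SAP 8.2.3 already analyses FU symptoms with rescue as failure, and SAP 7.1.3 tabulates rescue by timing. Women rescued by TOC complete TOC procedures, so their failure normally still shows in the Baseline-to-TOC ANCOVA. All of this stands, and it is why the point is minor.

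A second reply is that the gaps in the working do not measure bias. They compare two estimands on assumed scores, and other rescue strategies are defensible. This also stands. A reader might take 1.1 points as the size of the error, or as its maximum. The documents support neither: the figure assumes that rescued women had not improved at all, whereas the example trigger in Protocol 11.4 is only a symptom score of 3 or more, and higher placebo rescue would exceed it.

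A third reply is that Protocol 14.11 already asks for signs to be rated before rescue, and Protocol 14.8 requires the triggering symptom rating to be documented. That makes the worst case for late rescue unlikely. It does not help women who have no FU visit, and the SAP does not say which rating to use.

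**Conclusion.** The gap is real. Followed as written, the plan normally removes women rescued by TOC from the FU score comparison and lets ratings made after rescue count as outcomes at either visit. The SAP's own binary endpoints treat these women as failures. If rescue is commoner on placebo, the likely bias is towards no effect; if rescue rates are similar, the distortion may be negligible. The size cannot be derived, since neither a placebo rescue rate nor any score mean is given.

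Three stronger readings are not supported:
- That the primary result is at risk. SAP 8.1 has its own rescue rule, and SAP 4.4 covers its missing data.
- That FU scores should also be replaced after topical non-antifungal use. The early-termination provision in Protocol 11.4 concerns antifungal rescue, so those women still have an FU visit and a valid score.
- That multiple imputation of other missing scores is needed. That is a separate choice and does not follow from this gap.

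Severity is minor, and the repair is a cheap improvement.

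**What to change.** Before unblinding, add to SAP 8.2.5, for both ANCOVAs:

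> For a subject who takes antifungal rescue prior to or at the visit analysed, the score is the complete composite score rated before rescue at the visit where rescue was started, or at the early-termination visit. If there is none, it is her baseline score. Ratings made after rescue, including a zero derived because no signs were rated, are not used in the main analysis. An FU visit that did not take place is not coded as zero.

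Then:
- define this rule as the mBOCF already in the abbreviation list, or delete that abbreviation;
- keep the observed-case ANCOVA as a sensitivity analysis;
- show by arm the number analysed and the number whose score was set by the rule;
- list the change in SAP section 11, since it departs from the protocol's no-imputation rule.

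Scores missing for reasons other than rescue stay as now planned. This strategy is suggested because it matches SAP 8.2.3 and uses ratings already collected. Using outcomes after rescue would need FU visits that Protocol 11.4 does not require.

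The cost is one paragraph, one derivation and one section 11 entry, with no new data. There is a downside: mean improvement will look smaller in each arm, and a woman rescued without a prior rating is set to zero change even if she had partly improved.
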